7.2. Setting

The study will be conducted with the Audifarma patient cohort that meets the inclusion and exclusion criteria between the periods from January 2013 to June 30, 2018. The follow up period will be among January 2013 to July 2019, to ensure that the last patients can provide follow-up for one year.

This study will include the entire population in which medical records can be accessed. This will depend on the authorization of the HMOs for review of medical records. Participating patients will be followed-up until the patient has a stroke/systemic embolism, major bleeding, discontinuation, change of treatment or until the data collection period is completed.

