6. RESEARCH QUESTION AND OBJECTIVES

Primary Objectives

- To assess demographic and clinical characteristics of NVAF patients treated with oral anticoagulants (OACs) in Colombia.
- To describe treatment patterns (eg. OAC usage, dose, concomitant medications, persistence)

Exploratory Objectives

- To descriptively assess the time to clinical events (Effectiveness and Safety Outcomes) among patients persistent on OAC therapy.

Effectiveness outcomes: First Stroke/ Systemic Embolism; CCI

Safety outcomes: Major bleeding, CCI

[figure not shown]

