Persistence	Clinical outcome	Claim databases	Yes, No
OAC treatment	Treatment	Claim databases	Warfarin, apixaban, rivaroxaban, dabigatran
Diagnosis at index date	Treatment	Claim databases	Diagnosis AF based on ICD-10
Date of OAC prescription	Treatment	Claim databases	Date reported dd/mm/yy
Dosage of the initial OAC treatment	Treatment	Claim databases	Mg per dose
Initial frequency of OAC treatment	Treatment	Claim databases	Number of doses at initial OAC treatment
OAC escalation	Treatment	Claim databases	Yes, No
Type of OAC escalation	Treatment	Claim databases	Dose increase or dose decrease
Time to OAC escalation	Treatment	Claim databases	Date reported dd/mm/yy
CCI			

Variable	Role	Data source (s)	Operational definition
CCI			
INR testing monthly in patients with warfarin	Treatment	Medical record	INR reported in the medical record per month
Switch to another OAC treatment:	Treatment	Claim databases	Yes, No
Time to Switch to another OAC treatment	Treatment	Claim databases	Date reported dd/mm/yy
Causa de cambio	Treatment	Medical record	Adverse events, effectiveness, adherence, patient preference, administrative problems, not reported, others
Concomitant therapies by OAC prescription	Treatment	Medical record	NSAIDs, Angiotensin-converting-enzyme (ACE) inhibitors, Amiodarone, Beta-blockers, Angiotensin II receptor blockers (ARBs), Aspirin, Clopidogrel, Digoxin, Diuretics, calcium blockers, statins, proton pump inhibitor, selective H2 antagonists, antidiabetics, insulin, serotonin reuptake inhibitors
Previously exposed to warfarin	Treatment	Claim databases	Yes, No

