7.4.1. Claim Database

Claim databasee contains all prescriptions of all patients' medications chronologically. From this database, the index date will be established and the diagnosis of NVAF of the patient will be extracted. Similarly, this base will be used to assess the persistence on therapy and treatment patterns (duration of treatment, changes, persistence), pharmacy claim information, demographic information, diagnosis and insurance data.

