7.6.4 Collection of Information

For the analysis of the data, the statistical package Statistical Package for the Social Sciences (SPSS) Statistics, version 26.0 (IBM, US) for Windows will be used.

Data collection will be performed by healthcare providers following a data collection template developed in Microsoft Excel. For the purpose of unifying criteria and concepts, the template will be parametrized according to the possible responses or options for each variable, which will be defined by the medical expertise, information availability and published clinical studies. The template will be then validated according to a pilot testing of 20 randomly selected clinical charts.

Data collection will be performed after verifying the inclusion and exclusion criteria by the investigation staff. Firstly, the data regarding demographic data and delivery of the medications of interest to the patients meeting the criteria will be reviewed and collected. Subsequently, the electronic medical chart will be reviewed for collecting the clinical data will be identified.

In order to ensure protection of the patient's personal data and maintain high confidentiality and protection of the personal data according to the corporative policy 404 on *Protecting the Privacy of Personal Data*, the vendor will not transfer the collected database.

Pfizer will monitor the vendor to ensure the protection of the patient's personal data.

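### Section 7.2 limits the study to patients whose HMO authorises chart review, although OAC drug, dose, switch and persistence come from claims and other sections describe the full claims population

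*Combined protocol and SAP*

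**What the plan says.** **Population.** Section 7.2 states: "This study will include the entire population in which medical records can be accessed". It adds: "This will depend on the authorization of the HMOs for review of medical records". Access does not appear among the eligibility criteria in 7.2.1 and 7.2.2. The abstract and section 7.5 say that everyone treated with an OAC in the identification period is analysed in the claims database. Section 7.1 includes all initiators in that period and classes patients without access to the record as missing, together with losses to follow-up and changes of HMO. Section 7.7.1 restricts analyses to observed cases.

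**Objective and sources.** The second primary objective (section 6) reads: "To describe treatment patterns (eg. OAC usage, dose, concomitant medications, persistence". Section 7.4.1 takes the index date and the NVAF diagnosis from claims and says that "this base will be used to assess the persistence on therapy and treatment patterns". Table 1 agrees for persistence ("Persistence Clinical outcome Claim databases") and gives the same source for OAC drug, dose, frequency, dose change and switch. It sends other treatment variables to the chart: "Concomitant therapies by OAC prescription Treatment Medical record", and likewise monthly INR and the reason for a switch.

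**Order of work.** Under 7.6.4, once the criteria have been verified, "the data regarding demographic data and delivery of the medications of interest to the patients meeting the criteria will be reviewed and collected". The electronic chart is reviewed after that.

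**The concern.** As 7.2 is worded, an eligible patient with a full dispensing history leaves the study because an HMO declines chart review. That patient's OAC drug, dose, dose change and switch are nevertheless available in claims, as are the supply gaps that define discontinuation. Whether the patient stays in is decided by the HMO and not by an eligibility criterion. If persistence or the mix of drugs and doses differs between HMOs that authorise and those that do not, the estimates describe the authorising HMOs only.

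The plan would not reveal such a difference. It schedules no comparison of patients with and without a chart, and the limitations in 7.9 do not mention this selection. Because 7.2 conflicts with the abstract, 7.1 and 7.5, two analysts could also report persistence on different denominators and each cite the protocol.

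**Working it through.** **1. The plan's own figure.** Section 7.5 gives 7,500 patients, a database count of patients verified against the inclusion criteria. No precision, power or effect size lies behind it, so there is nothing to reproduce. The count is reported in the past tense, while 8.3 places HMO authorisation in the future, after ethics committee support. It therefore probably precedes chart access, but that is an inference.

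**2. Which parts of the objective need a chart.**

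| Element | Source in the plan |
|---|---|
| OAC drug, dose, frequency, dose change, switch | Claims (Table 1) |
| Persistence: switch or 60-day supply gap | Claims (Table 1, 7.3.1, 7.4.1) |
| Persistence: censoring when follow-up ends at death, stroke/systemic embolism or major bleeding | Chart (7.1 and 7.3.1 for the rule; abstract, Data sources, for the events) |
| Concomitant therapies, monthly INR, reason for switch | Chart (Table 1) |

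The restriction is therefore avoidable for the first two rows. It is not avoidable, as the plan stands, for the last two.

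**3. Illustrative size.** Let *a* be the share of eligible patients with an accessible chart, and *d* the difference in the proportion persistent between accessible and inaccessible patients. The full-population value is a × P(accessible) + (1 − a) × P(inaccessible), so restricting to accessible patients gives

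bias = (1 − a) × d.

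The 95% half-width at a proportion of 50% is 1.96 × √(0.25/n), with n = 7,500 × a. Both *a* and *d* are assumptions; the documents give neither.

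| a | n | Half-width (points) | Bias, d = 2 | Bias, d = 5 | Bias, d = 10 |
|---|---|---|---|---|---|
| 100% | 7,500 | 1.13 | 0 | 0 | 0 |
| 90% | 6,750 | 1.19 | 0.2 | 0.5 | 1.0 |
| 70% | 5,250 | 1.35 | 0.6 | 1.5 | 3.0 |
| 50% | 3,750 | 1.60 | 1.0 | 2.5 | 5.0 |

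Lost precision is minor: from 1.13 to 1.60 points when half the charts are closed. Bias exceeds the half-width when d is above half-width/(1 − a): 1.19/0.10 = 11.9 points at 90% access, 1.35/0.30 = 4.5 at 70%, and 1.60/0.50 = 3.2 at 50%. If 7,500 is in fact the count after chart access, the half-width is 1.13 throughout and the bias columns do not change.

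**The case against.** The strongest reply is that 7.2 is not the whole plan. Access is absent from the eligibility criteria, and the abstract, 7.1 and 7.5 describe the full claims population. If patients without a chart are only missing, and analyses use observed cases, their claims data could stay in the claims-based analyses. This stands to the extent that exclusion is not settled. It does not remove the problem, because 7.2 says the opposite and no analysis set is defined.

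The second reply concerns the sources. A reader might infer that persistence and treatment patterns come entirely from claims, so that complete data are being discarded. The documents do not support that. Concomitant therapies, INR and reason for switch are chart variables, even though 7.4.1 suggests that concomitant drugs could be read from claims. Persistence as planned is censored at the end of follow-up, which can be a chart-recorded event. Without a chart, a patient who dies, or stops after a bleed, looks like a 60-day-gap discontinuation. Claims-only persistence is thus a different quantity. Comparing it with chart-censored persistence could show a difference where there is no selection at all.

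The third reply is that the magnitude is assumed throughout. This is correct: at 90% access and a 2-point difference the bias is 0.2 points, well inside sampling error.

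**Conclusion.** The point holds for OAC drug, dose, dose change, switch and the claims-defined part of persistence. As 7.2 is written, they are estimated in a subset selected by HMO, without need and without a check, and the other sections contradict 7.2 on who is in the study.

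The size is unknown. The range of 0.2 to 5 points rests on assumed access of 90% to 50% and assumed differences of 2 to 10 points. It shows only that the bias could be negligible or could be about three times the half-width (5.0/1.60 = 3.1).

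A reader might go further and infer that the results will be biased by a definite amount, that HMOs are known to differ in ways that affect persistence, or that only patients still affiliated when charts are read will be kept. The documents give no access share and no data by HMO. Section 7.1 lists change of HMO among the missing, which is compatible with the last inference but does not establish it. This should be fixed before analysis, but it does not invalidate the study.

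**What to change.** Reconcile the abstract, 7.1, 7.2 and 7.5 by defining two analysis sets.

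- **Set 1:** all patients meeting the criteria in claims. Use it for OAC drug, dose, dose change, switch and a claims-only persistence measure that ends at a switch or 60-day gap and is censored at the end of claims data.
- **Set 2:** patients with an accessible chart. Use it for chart-based characteristics, concomitant therapies, INR, reason for switch, clinical events, and persistence with censoring at clinical events as now planned.

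Report the number without chart access by HMO, and say whether the 7,500 was counted before or after access. Compare index OAC, index dose, index year and claims age and sex by chart access. Compare persistence between the two groups only under the claims-only rule, applied identically to both. Add this selection to 7.9.

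**Cost.** No new data are needed; section 7.4.1 says that claims hold demographic, diagnosis and insurance data. The report carries two denominators. Annex 1 lists no stand-alone SAP, so the change is to protocol wording, and under 8.3 amendments need ethics committee approval. In set 1 the exclusions rest on claims diagnoses alone, and the exclusion for transitory NVAF has no code list. Deaths, or stops after a clinical event, may count there as discontinuation, which is why the planned persistence analysis should be kept in set 2.

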7.2.1. Inclusion Criteria

Patients must meet all of the following inclusion criteria to be eligible for inclusion in the study:

- a) Patients with a diagnosis of AF considered according to the following diagnoses as per the ICD I48 codes at some point before or on the index date, without recorded valvular disease;
- b) Patients who have started treatment with apixaban, dabigatran, rivaroxaban and warfarin for the first time during the identification period, understanding as start of drug delivery by insurer, and after the diagnosis of AF between January 1, 2013 to June 30, 2018;
- c) Patients starting apixaban, dabigatran, rivaroxaban from January 1, 2013 to June 30, 2018 in patients previously exposed to warfarin;
- d) Patient had continuous health plan for 6 months pre-index date (baseline period);
- e) Patients older than 18 years old on the index date;
- f) NVAF diagnosis before or on the index date

7.2.2. Exclusion Criteria

Patients meeting any of the following criteria will not be included in the study:

- e) Patients with any of the following diagnoses prior to the use of the treatments of interest or index date:
 - Valvular heart disease or valve replacement – ICD-10 codes: I05, I06, I07, I08, I09, I22, I34, I35, I36, I37, I38, I39, I700, I702-I709; Q22, Q23, Q25, T82,Z95.
 - Pregnancy during the study period. ICD-10 O00-O9A
 - Diagnosis of venous thromboembolism (VTE) – ICD-10 codes: I26, I80 - I82;
- f) Individuals with a transitory diagnosis of NVAF prior to the use of the treatments of interest or index date;
- g) Exposure to more than one OAC on or after the index date, during the follow-up period.
- h) NOAC doses different from those recommended by the manufacturing laboratories.

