Observational, descriptive study of a retrospective cohort of adult patients diagnosed with NVAF in selected Health Maintenance Organizations (HMO) of Colombia. These patients will be identified from the drug claim database, whose index date of the study will be the first prescription with any of the oral anticoagulants, that is, they are patients with NVAF for the first time starting a therapy with any of the NOACs between January 1, 2013 and June 30, 2018 and follow up period will be among January 2013 to July 2019, to ensure that the last patients can provide follow-up for one year. Patients will be required to have an NVAF diagnosis before or on the index date and health plan for 6 months pre-index date (baseline period).

Population:

The total population of patients treated with any oral anticoagulant between January 1, 2013 and June 30, 2018 will be analyzed in the claim database. This means that patients who start warfarin and NOACs would be included within this period. Patients who initiate NOACs within the established period and who have been exposed to warfarin before 2013 will also be included.

Inclusion criteria:

Patients must meet the following inclusion criteria in order to be able to take part in the study:

- Patients with a diagnosis of AF considered according to the following diagnoses as per the 10th revision of the International classification of diseases (ICD-10) I48 codes at some point before or on the index date, without recorded valvular disease;
- Patients who have started treatment with apixaban, dabigatran, rivaroxaban and warfarin for the first time during the identification period, understanding as start of drug delivery by insurer, and after the diagnosis of AF between January 1, 2013 to June 30, 2018;
- Patients starting apixaban, dabigatran, rivaroxaban from January 1, 2013 to June 30, 2018 in patients previously exposed to warfarin;
- Patient had continuous health plan enrolment for 6 months pre-index date (baseline period);
- Patients older than 18 years old on the index date;
- NVAF diagnosis before or on the index date.

Exclusion criteria:

Patients who meet any of the following criteria will not be included in the study:

- Patients with any of the following diagnoses prior to the use of the treatments of interest or index date:
 - Valvular heart disease or valve replacement – ICD-10 codes: I05, I06, I07, I08, I09, I21, I22, I34, I35, I36, I37, I38, I39, I700, I702-I709; Q22, Q23, Q25, T82, Z95

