K272	Acute with both haemorrhage and perforation
K274	Chronic or unspecified with haemorrhage
K276	Chronic or unspecified with both haemorrhage and perforation
K280	Acute with haemorrhage
K282	Acute with both haemorrhage and perforation
K284	Chronic or unspecified with haemorrhage
K286	Chronic or unspecified with both haemorrhage and perforation
K290	Acute haemorrhagic gastritis
K625	Haemorrhage of anus and rectum
K920	Haematemesis
K921	Melaena
K922	Gastro-intestinal haemorrhage, unspecified
D62	Acute posthaemorrhagic anaemia
H356	Retinal haemorrhage
H431	Vitreous haemorrhage
H450	Vitreous haemorrhage in diseases classified elsewhere
H922	Otorrhagia
I312	Haemopericardium, not elsewhere classified
J942	Haemothorax
R04	Haemorrhage from respiratory passages
K661	Haemoperitoneum
M250	Haemarthrosis
N02	Recurrent and persistent haematuria
N938	Other specified abnormal uterine and vaginal bleeding
N939	Abnormal uterine and vaginal bleeding, unspecified
N950	Postmenopausal bleeding
R31	Unspecified haematuria
R58	Haemorrhage, not elsewhere classified
T792	Traumatic secondary and recurrent haemorrhage

- Ischemic stroke:** Patients who report the following diagnoses in the medical history during the follow-up period:

ICD-10	Description
I63	Cerebral infarction
I64	Stroke, not specified as haemorrhage or infarction

Except I63.6 Cerebral infarction due to thrombosis of cerebral veins, non-pyogenic

- Hemorrhagic stroke:** Patients presenting the following diagnosis in the medical record:

PFIZER CONFIDENTIAL

ICD-10	Description
I60	Subarachnoid haemorrhage
I61	Intracerebral haemorrhage
I62	Other nontraumatic intracranial haemorrhage

- **Systemic embolism:** Patients who report any of the following diagnoses:

ICD-10	Description
I74	Arterial embolism and thrombosis

Definition of covariates

- **Age:** Categorical variable, continues in years. It will be defined from the index date and will be used to assign patients to the following age categories:

18 - 49
 50 - 59
 60 - 69
 70 - 79
 ≥ 80 years old.

- **Charlson Index:** Charlson comorbidity index will be created during the reference period taking into account the following score:

1 point each:

- *Myocardial infarction*

ICD-10	Description
I21	Acute myocardial infarction
I22	Subsequent myocardial infarction
I252	Old myocardial infarction

- *Congestive heart failure*

ICD-10	Description
I110	Hypertensive heart disease with (congestive) heart failure

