I130	Hypertensive heart and renal disease with (congestive) heart failure
I132	Hypertensive heart and renal disease with both (congestive) heart failure and renal failure
I110	Hypertensive heart disease with (congestive) heart failure

- *Peripheral vascular disease*

ICD-10	Description
I70	Atherosclerosis
I71	Aortic aneurysm and dissection
I731	Thromboangiitis obliterans [Buerger]
I738	Other specified peripheral vascular diseases
I739	Peripheral vascular disease, unspecified

PFIZER CONFIDENTIAL

ICD-10	Description
I771	Stricture of artery
I790	Aneurysm of aorta in diseases classified elsewhere
I792	Peripheral angiopathy in diseases classified elsewhere
K551	Chronic vascular disorders of intestine
K558	Other vascular disorders of intestine
K559	Vascular disorder of intestine, unspecified
Z958	Presence of other cardiac and vascular implants and grafts
Z959	Presence of cardiac and vascular implant and graft, unspecified

▪ *Dementia*

ICD-10	Description
F00	Dementia in Alzheimer's disease
F01	Vascular dementia
F02	Dementia in other diseases classified elsewhere
F03	Unspecified dementia
G30	Alzheimer's disease
F051	Delirium superimposed on dementia
G311	Senile degeneration of brain, not elsewhere classified

▪ *Cerebrovascular disease*

ICD-10	Description
G45	Transient cerebral ischaemic attacks and related syndromes
G46	Vascular syndromes of brain in cerebrovascular diseases
I60	Subarachnoid haemorrhage
I61	Intracerebral haemorrhage
I62	Other nontraumatic intracranial haemorrhage
I63	Cerebral infarction
I64	Stroke, not specified as haemorrhage or infarction
I65	Occlusion and stenosis of precerebral arteries, not resulting in cerebral infarction
I66	Occlusion and stenosis of cerebral arteries, not resulting in cerebral infarction
I67	Other cerebrovascular diseases
I68	Cerebrovascular disorders in diseases classified elsewhere
I69	Sequelae of cerebrovascular disease
H340	Transient retinal artery occlusion

▪ *Chronic pulmonary disease*

ICD-10	Description
J40	Bronchitis, not specified as acute or chronic
J41	Simple and mucopurulent chronic bronchitis
J42	Unspecified chronic bronchitis
J43	Emphysema
J44	Other chronic obstructive pulmonary disease
J45	Asthma
J46	Status asthmaticus
J47	Bronchiectasis
J60	Coalworker's pneumoconiosis
J61	Pneumoconiosis due to asbestos and other mineral fibres
J62	Pneumoconiosis due to dust containing silica

PFIZER CONFIDENTIAL

ICD-10	Description
J63	Pneumoconiosis due to other inorganic dusts
J64	Unspecified pneumoconiosis

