H: I10, I11, I12, I13, I15

Score 1 point

ICD-10	Description
I10	Essential (primary) hypertension
I11	Hypertensive heart disease
I12	Hypertensive renal disease
I13	Hypertensive heart and renal disease
I15	Secondary hypertension

A: Age \geq 75 years

Score 2 points

D: E10 a E14

Score 1 point

ICD-10	Description
E10	Insulin-dependent diabetes mellitus
E11	Non-insulin-dependent diabetes mellitus
E12	Malnutrition-related diabetes mellitus
E13	Other specified diabetes mellitus
E14	Unspecified diabetes mellitus

S2: G45.0, G45.1, G45.2, G45.3, G45.8, G45.9

Score 2 points

ICD-10	Description
G450	Vertebral-basilar artery syndrome
G451	Carotid artery syndrome (hemispheric)
G452	Multiple and bilateral precerebral artery syndromes
G453	Amaurosis fugax
G458	Other transient cerebral ischaemic attacks and related syndromes

V: I26, I82, I21- I25, I65, I70- I72, I73.1, I73.8, I73.9, I79.0, I79.2, K55.1, K55.8, K55.9, Z95.8, Z95.9

Score 1 point

ICD-10	Description
I26	Pulmonary embolism
I82	Other venous embolism and thrombosis
I21	Acute myocardial infarction
I22	Subsequent myocardial infarction
I23	Certain current complications following acute myocardial infarction
I24	Other acute ischaemic heart diseases
I25	Chronic ischaemic heart disease
I65	Occlusion and stenosis of precerebral arteries, not resulting in cerebral infarction
I70	Atherosclerosis
I71	Aortic aneurysm and dissection
I72	Other aneurysm
I731	Thromboangiitis obliterans [Buerger]
I738	Other specified peripheral vascular diseases
I739	Peripheral vascular disease, unspecified
I790	Aneurysm of aorta in diseases classified elsewhere
I792	Peripheral angiopathy in diseases classified elsewhere
K551	Chronic vascular disorders of intestine
K558	Other vascular disorders of intestine

A: Age 64-74 years

Score 1 point

Sc: Sex category (female)

Score 1

- **HASBLED score:** The HAS-BLED score will be used to analyze the risk of bleeding. The modified HAS-BLED score ranges from 0 to 8. ICD-10 diagnostic codes for each component of the index when applicable:

•

H: I10, I11, I12, I13, I15

Score 1 point

ICD-10	Description
I10	Essential (primary) hypertension
I11	Hypertensive heart disease
I12	Hypertensive renal disease
I13	Hypertensive heart and renal disease
I15	Secondary hypertension

Apixaban

B0661148- NON-INTERVENTIONAL STUDY PROTOCOL

Final, 10 October 2019

A: N03.2, N03.3, N03.4, N03.5, N03.6, N03.7, N05.2, N05.3, N05.4, N05.5, N05.6, N057, N18- N19, N25.0, Z49.0, Z49.2, Z94.0, Z99.2

Score 1 point

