Peripheral artery disease	I702 Atherosclerosis of arteries of the extremities I708 Atherosclerosis of other arteries I709 Generalised and unspecified atherosclerosis
Anaemia	D50 Iron deficiency anaemia D51 Vitamin B12 deficiency anaemia D52 Folate deficiency anaemia D53 Other nutritional anaemias D55 Anaemia due to enzyme disorders D56 Thalassaemia D57 Sickle-cell disorders D58 Other hereditary haemolytic anaemias D59 Acquired haemolytic anaemia
Congestive heart failure	I110 Hypertensive heart disease with (congestive) heart failure I130 Hypertensive heart and renal disease with (congestive) heart failure I132 Hypertensive heart and renal disease with both (congestive) heart failure and renal failure
Renal disease	B15 Acute hepatitis A B16 Acute hepatitis B B17 Other acute viral hepatitis B18 Chronic viral hepatitis B19 Unspecified viral hepatitis C22 Malignant neoplasm of liver and intrahepatic bile ducts K70 Alcoholic liver disease K71 Toxic liver disease K72 Hepatic failure, not elsewhere classified K73 Chronic hepatitis, not elsewhere classified K74 Fibrosis and cirrhosis of liver

PFIZER CONFIDENTIAL

Variable	Operacional definition ICD-10
	K75 Other inflammatory liver diseases K76 Other diseases of liver K77 Liver disorders in diseases classified elsewhere Z944 Liver transplant status
Myocardial infarction	I21 Acute myocardial infarction I22 Subsequent myocardial infarction I252 Old myocardial infarction
Peripheral vascular disease	I70 Atherosclerosis I71 Aortic aneurysm and dissection I731 Thromboangiitis obliterans [Buerger] I738 Other specified peripheral vascular diseases I739 Peripheral vascular disease, unspecified I771 Stricture of artery I790 Aneurysm of aorta in diseases classified elsewhere I792 Peripheral angiopathy in diseases classified elsewhere K551 Chronic vascular disorders of intestine K558 Other vascular disorders of intestine K559 Vascular disorder of intestine, unspecified Z958 Presence of other cardiac and vascular implants and grafts Z959 Presence of cardiac and vascular implant and graft, unspecified
TIA	G450 Vertebro-basilar artery syndrome G458 Other transient cerebral ischaemic attacks and related syndromes G451 Carotid artery syndrome (hemispheric) G459 Transient cerebral ischaemic attack, unspecified
Coronary artery disease	I20 Angina pectoris I21 Acute myocardial infarction

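### The valve-disease exclusion differs by I21 between the abstract and section 7.2.2, and both lists contain codes that the protocol itself labels as infarction or atherosclerosis

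*Combined protocol and SAP*

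**What the plan says.** The exclusion appears twice under the same heading, which names valvular heart disease or replacement of a valve. It applies to diagnoses recorded before treatment or the index date.

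- Abstract (section 2): "I05, I06, I07, I08, I09, I21, I22, I34, I35, I36, I37, I38, I39, I700, I702-I709; Q22, Q23, Q25, T82, Z95".
- Section 7.2.2: I05 to I09, then "I22, I34, I35, I36, I37, I38, I39, I700, I702-I709; Q22, Q23, Q25, T82,Z95".

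Inclusion criterion a) in section 7.2.1 asks for an atrial fibrillation code "at some point before or on the index date, without recorded valvular disease". It sets no condition on vascular disease.

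Other parts of the protocol use several of the excluded codes to define baseline conditions:

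- The Charlson index and Table 2 place I21, I22 and I252 under myocardial infarction. The label of I22 is "Subsequent myocardial infarction".
- Table 2 defines peripheral artery disease as "I702 Atherosclerosis of arteries of the extremities I708 Atherosclerosis of other arteries I709 Generalised and unspecified atherosclerosis".
- The Charlson index and Table 2 label I70 as atherosclerosis, under peripheral vascular disease. The same group contains Z958, labelled "Presence of other cardiac and vascular implants and grafts", and Z959, its unspecified counterpart.
- The vascular item of CHA2DS2-VASc is "V: I26, I82, I21- I25, I65, I70- I72, I73.1, I73.8, I73.9, I79.0, I79.2, K55.1, K55.8, K55.9, Z95.8, Z95.9".

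The first primary objective in section 6 is "To assess demographic and clinical characteristics of NVAF patients treated with oral anticoagulants (OACs) in Colombia".

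**The concern.** There are two defects. First, the lists disagree on I21, and a programmer cannot follow both. Section 3 records no amendments and the protocol is version 1.0, so no superseded text explains the difference.

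Second, a line headed as a valve exclusion also removes patients with certain infarction and atherosclerosis codes. The plan sets out to describe those same conditions: Table 1 has rows for myocardial infarction and peripheral vascular disease, and the vascular item scores them. If the screen removes some of these patients first, reported vascular comorbidity is too low for the NVAF population named in the objective. A reader would have no notice of this, because neither the eligibility text nor the limitations in section 7.9 mentions a vascular restriction.

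**Working it through.** The plan gives no figure to reproduce. The check compares the two lists with each other and with the protocol's own code definitions.

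**Step 1: the two lists.** Counting I702-I709 as one entry, section 7.2.2 has 19 entries and the abstract has 20. Expanding that range to its 8 codes gives 19 - 1 + 8 = 26 and 20 - 1 + 8 = 27. The abstract minus 7.2.2 is {I21}; 7.2.2 minus the abstract is empty.

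**Step 2: labels given in the protocol.**

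- I21 (abstract only) and I22 (both lists): myocardial infarction.
- I702, I708 and I709: each labelled individually in Table 2 as a form of atherosclerosis.
- I700 and I703 to I707: no label of their own, only the parent I70, atherosclerosis.
- Z95: no label as a parent. Z958 and Z959 are labelled as cardiac and vascular implants and grafts, which does not rule out a valve.

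I701 is in neither list, so I70 is excluded only in part.

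**Step 3: overlap with the planned baseline variables.** A code counts as excluded if it, or its parent, is on the list.

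| Variable | Codes | Wholly excluded, 7.2.2 | Wholly excluded, abstract | In part |
|---|---|---|---|---|
| Peripheral artery disease (Table 2) | 3 | 3 | 3 | none |
| Myocardial infarction | 3 | 1 (I22) | 2 (I21, I22) | none |
| Peripheral vascular disease | 13 | 2 (Z958, Z959) | 2 (Z958, Z959) | I70 |
| Vascular item of CHA2DS2-VASc | 19 | 3 (I22, Z958, Z959) | 4 (also I21) | I70 |

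The vascular item has 21 codes. I26 and I82 are left out here because the separate venous thromboembolism exclusion removes them: 21 - 2 = 19. Untouched codes are 13 - 2 - 1 = 10 for peripheral vascular disease, and 19 - 3 - 1 = 15 (7.2.2) or 19 - 4 - 1 = 14 (abstract) for the vascular item. These are code counts, not patient counts.

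**Step 4: what could happen to a reported prevalence.** The documents give no prevalence and no counts per code, so both inputs are assumptions. Let p be the true prevalence of a vascular condition among otherwise eligible patients, and f the share of those patients who carry an excluded code. If the codes remove only patients with the condition, then

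observed prevalence = p(1 - f) / (1 - pf).

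| p | f = 10% | f = 50% | f = 90% |
|---|---|---|---|
| 5% | 4.5% | 2.6% | 0.5% |
| 10% | 9.1% | 5.3% | 1.1% |
| 20% | 18.4% | 11.1% | 2.4% |

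For example, with p = 10% and f = 50%: 0.10 × 0.50 / (1 - 0.05) = 0.05 / 0.95 = 5.3%. Under these assumptions the bias is always downward, but its size ranges from slight to nearly total.

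**The case against.** The strongest reply is that the effect is unknown and may be small. Section 7.2.2, the operative text, excludes only one of three infarction codes, and I701 and most vascular codes are untouched. Table 1 takes infarction and peripheral vascular disease from the medical record as yes or no, so a patient with charted disease but no excluded code can still enter. The study is descriptive and section 7.7 rules out a treatment comparison, so no treatment effect is at stake. All of this stands. It limits the size that can be claimed, but it neither resolves the I21 contradiction nor explains vascular codes under a valve heading.

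A reader might go further and infer that Table 2 peripheral artery disease must be zero by construction. The documents do not support that. Patients are identified in claims (section 7.4.1) and characterized from charts (section 7.4.2), and the plan does not say which records the exclusion screen uses. The variable is empty for pre-index codes only if the screen and the variable draw on the same records. A code first recorded on the index date could also remain. Table 1 has no peripheral artery disease row.

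A reader might also infer that Z958 and Z959 are plainly non-valvular and should be deleted. Their labels include cardiac implants, so they may cover valves. Deleting them outright could admit patients whom the heading is meant to exclude.

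**Conclusion.** The concern holds. Eligibility of a patient with a prior I21 code is contradictory, and both lists carry infarction and atherosclerosis codes, by the protocol's own labels, under a valve heading without a stated reason. Followed as written, the cohort under-represents patients with coded vascular disease, which bears directly on the first primary objective. Vascular disease is depleted, not eliminated.

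The number of patients lost cannot be computed, and no shift in CHA2DS2-VASc or the Charlson index can be asserted. For I700 and I703 to I707, the conclusion rests on the parent label alone. The two textual defects hold whatever the prevalence; the prevalence table is illustrative only.

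**What to change.** - Put one identical code list in the abstract and in section 7.2.2.
- Remove I21, I22, I700 and I702 to I709 from the valve line. If a vascular exclusion was intended, give it its own heading and reason, and restrict the conclusions and the affected baseline variables to match.
- Check every remaining code against the heading. For Z95, including Z958 and Z959, justify the entry or narrow it to what the heading covers.
- State which records are screened, apply the corrected list before chart abstraction, and report the number excluded per code.

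The edit itself is small. Sections 7.1 and 7.6.4 place the eligibility check before data collection, so the corrected list can be applied at that step. Section 7.5 speaks of 7,500 patients already verified, but only against the inclusion criteria. If the exclusions had also been applied, selection must be re-run. Either way there may be more charts for the physicians to abstract, by a number that the documents do not give, within the planned window of November 15, 2019 to March 31, 2020.
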